5.1 Study deviations

During the study, any deviations from the signed protocol will be noted and highlighted in the study report.

5.2 Ethical considerations

Each participant will be asked to read, sign and date an informed consent form, including information on confidentiality agreement, audio video release and adverse events reporting. Adolescents and children will be asked to sign the relevant informed assent form. A blank copy of the consent forms and assent forms can be found in the appendices. Participants will only be allowed to participate in their sessions following their informed consent/ assent to do so. The participants will be screened with the help of a recruitment questionnaire to make sure that they qualify for the study using a pre-defined list of screening criteria. The sessions will be moderated by a Senior Consultant at PA who has experience in conducting usability studies

Due to the nature of the study and material used ethical approval is not considered necessary for this study.

5.3 Confidentiality of participant information

Only PA employees who are involved with the project will have access to this data. Participants' data will not be linked to their personal details and only fully anonymized data will be reported to the DHSC All audio-visual recordings will be used for research purposes only by PA and DHSC and will not be passed to a third party.

Data will be controlled in accordance to current GDPR guidelines

5.4 Risks to participants

Participants will be exposed to minimal risks during the usability test session. The minimal risk could include discomfort when taking the sample in the throat or nose, participants might become fatigued by the study's endpoint or might experience negative emotions, such as frustration and annoyance when trying to use the test kit or are disappointed if they receive a positive result.

Participants will be advised that if they have any concerns or experience distress during the study, to tell the Study Staff immediately.

In addition to the risks listed above, there may be some unknown or infrequent and unforeseeable risks associated with participating in this study. Participants will be informed in a timely manner both verbally and in writing of any new information, findings or changes to the way the research will be performed that might influence their willingness to continue with their participation in this study.

Study deliverables 6

[figure not shown]
The study deliverables will be:

- Study Protocol and supporting appendicesStudy report

Appendix 2 – Test kit

Appendix 3 – Participant screener

Participant Screener

This is a research study to gather user feedback on the use of coronavirus (COVID-19) test kit.

The research will be conducted in the UK remotely. We will do this by sending a link to join a remote viewing session, where the interviewer will run the session. We will also send materials that participants will need for the interview. This material we will fit into a large envelope. The envelope will contain webcam, test kit and prepaid envelope to be used to return the webcam. All test kit materials will be disposed of by the participant in their home.

For Tuesday – please recruit locally to enable hand delivery of supplies on the Monday 16th November 2020

Participants:

General UK population

Eligible for inclusion:

- Participants are willing to participate in a 1:1 session lasting approximately 60 minutes at their home via a remote platform
- Be willing and provide written informed consent (including audio and video data capture).
- Be able to participate in the study on between: Tuesday 17th November Saturday 21st November 2020 (remote UK)
- Have access to a computer or laptop
- Be able to be on their own in a room for the duration of the session without being interrupted
- Have good internet connection
- Be IT literate
- Have Google Chrome
- Have experience of using remote platforms such as Skype, Microsoft Teams, Zoom etc

Exclusion criteria

- Are unwilling to give written informed consent (including audio and video data capture).
- Do not have access to a computer or laptop with a camera
- Are not able to be on their own in a room for the duration of the session without being interrupted
- Are not IT literate
- Do not have google chrome
- Do not have experience of using remote platforms such as Skype, Microsoft Teams, Zoom etc.
- Do not have good internet connection

User group	Quota	Key comments
Adolescents 12-17	15 + 2 over-recruits	Parent/ guardian present in background whilst session in progress
Adults 18 and over	15 + 2 over-recruits	Broad range of ages to cover 18 through to older adults
Adults with a child aged 4-11 who they care for	15 + 2 over-recruits	Adult and a child aged 4-11 count as 1 for the quota
Adults who provide caregiver role to another adult and provide assistance	15 + 2 over-recruits	Adult and person they care for count as 1 for the quota

Participants

Target: 60 participants in total consisting of 15 participants from each of the 4 user groups detailed in the table

Device research.

Target - Male and female adolescent respondents, male and female adult respondents, Male or female respondents and their child, male or female respondents and the person they care for

Respondent Name

Address

City_____

31

_

Phone	Mobile
Phone	BIIDDIN

Email

Hello Mr./Ms. ______, I am calling on behalf of a company called PA Consulting Group, a design and development company in the UK. Today we are speaking to individuals with the aim for them to join an interview.

During the interview we will gather your views and feedback on the use of a test kit. We are interested in seeing how you would use the device and we will ask you to perform a test during the interview.

These discussions are being held strictly for research purposes and in confidence; no promotion or sales of any kind are involved. If you are chosen to participate, we will invite you to attend an interview lasting between 60 minutes. We will compensate you for your time and opinions. Are you happy for me to carry on?

- 1. Can I start by asking you your age.
- () 12-17
- () 18 to 35
- () 36 to 65
- () 65+

ATTEMPT TO RECRUIT A RANGE OF RESPONDENTS FROM 18-65+ FOR THE ADULTS 18 AND OVER USER GROUP.

- 2. Are you male or female
- () Male
- () Female

ATTEMPT TO RECRUIT 50% FEMALE AND 50% MALE RESPONDENTS

- 3. Do you have any children below the age of 12 living with you?
- () Yes
- () No
- 4. If yes to 3 What is the age of your child?
- () 4 12 Years old
- () < 4years old **NOT REQUIRED**

AT END OF A POSITIVE SCREENER CHECK IF WILLING TO DO A TEST ON YOUR CHILD

TARGET 15 TESTS WHERE TEST IS ADMINISTERED ON THE CHILD

- 5. Do you provide a caregiving role to another adult and provide assistance to them?
- () Yes
- () No
- 6. If yes to 5 Do you provide assistance in assisting them to take medication?
- ()Yes
- () No

TARGET 15 TESTS WHERE TEST IS ADMINISTERED ON THE ADULT DEPENDENT

- 7. Can you speak and read the English language?
- () Yes
- () No **TERMINATE**
- 8. Which is your dominant hand?
- () Right
- () Left
- 9. How is your eyesight?
- () Normal no correction required
- () Reading glasses
- () Distance glasses
- () Contact lenses
- () Colour blind (record type)
- () Impaired (record severity and impairment e.g. blurred vision, double vision etc)

- 10. Are you red-green color-blind?
- () Yes; please describe: [For info only]
- () No

ATTEMPT TO RECRUIT SOME VISUALLY IMPAIRED AND COLOUR BLIND RESPONDENTS

- 11. Do you have trouble remembering information, solving problems or concentrating?
- () Yes (record type and severity)

() No

ATTEMPT TO RECRUIT SOME RESPONDENTS WITH TROUBLE REMEMBERING INFORMATION IF POSSIBLE

12. Do you have trouble performing day to day tasks with your hands?() Yes (record open ended response, ask if diagnosed with physical related illness e.g. Rheumatoid arthritis))

() Difficulty picking up small objects from a flat surface e.g. coins, pen?

() Difficulty fastening buttons?

() Difficulty writing?

() Tremors

ATTEMPT TO RECRUIT SOME RESPONDENT WITH DEXTERITY ISSUES IF POSSIBLE

13. Do you have access to a computer or laptop with a camera? () Yes () No TERMINATE 14. Do you have a good internet connection at home? () Yes () No TERMINATE 15. What is your IT experience? Detail:.... 16. Do you have Google Chrome installed on your computer/ laptop? () Yes () No TERMINATE 17. What remote platforms have you used, if any? Detail: 18. Do you, or does anyone in your immediate family, work in the following industry? () Market research/ advertising [gather details and refer to PA for decision] 19. Ask as applicable - Are you willing to perform a test on child? () Yes () No 20. If no - are you willing to do a test on yourself? () Yes () No

21. Ask as applicable - Are you willing to perform a test on your dependent?

() Yes

() No

22. If no - are you willing to do a test on yourself?

() Yes () No

The interview will take place remotely using your computer and will last between 60 minutes. We will ask you to keep confidential the details discussed and ask you to sign a confidentiality agreement. We will send you an informed consent form to sign ahead of your participation so that you can make an informed decision. Are you willing to agree to confidentiality?

Please be aware that the interview will be videotaped and pictures will be taken to document the research and produce a transcript of your comments. Only members of the research team and the research sponsor will have access to the video, photographs and transcripts. None of these materials will be released to the public. Are you OK with this?

In compensation for your time and views you will receive £50 as an honorarium.

Would you like to participate?

Yes - Schedule interview

____No - Terminate

SCHEDULE AND RECORD INFORMATION ON FRONT OF SCREENER

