2.2 Objective

The primary objective of this study is to validate that the LFD kit is safe and effective to use by the intended user population in the intended use environment.

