2.6 Intended users

The intended users of the LFD kit are members of the general public. A self-test is expected to be performed from the age of 12. Tests on children below the age of 12 will be undertaken by an adult. Adult caregivers will also undertake the test on other adults who are unable to perform the test on themselves.

Intended User Groups	Experience
Adolescents (aged 12-17 years old)	Naive users to self-administer the test
Adults (aged 18 years old and above)	Naive users to self-administer the test
Adult caregivers for children	Naive users to administer the test on family members below the age of 12
Adult caregivers for adult dependants	Naive adult users to administer the test to other adults who are unable to self-test

Table 1 - Intended user groups

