3.6 Participants

The total sample size for this study will be 60 participants administering the test. There will be 4 user groups. A breakdown of composition of each group is detailed Table 4.

Table 4 - Study sample

User groups	Sample size
Adolescents between the age of 12 and 17	15
Adults aged 18+	15
Adults administering the test to an adult dependant	15 caregivers plus 15 dependants
Adults administering the test to a child under the age of 12	15 parents plus 15 children

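### The caregiver-for-child group is recruited at ages 4 to 11 only, so the study will have no data on children under 4, although its stated target is all children under 12

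*Protocol*

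**What the plan says.** The primary objective in section 2.2 is to "validate that the LFD kit is safe and effective to use by the intended user population in the intended use environment".

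**Children.** Section 2.6 gives the tested age range with an upper limit only: "Tests on children below the age of 12 will be undertaken by an adult". Table 1 describes the caregivers in the same way: "Naive users to administer the test on family members below the age of 12". Table 4 in section 3.6, which sets the study sample, lists "Adults administering the test to a child under the age of 12" with 15 parents and 15 children. The quota table in Appendix 3 instead reads "Adults with a child aged 4-11 who they care for", and screener question 4 carries the entry "< 4years old NOT REQUIRED". The other answer band in question 4 runs from 4 to 12.

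**Adolescents.** Section 2.6 states: "A self-test is expected to be performed from the age of 12". Table 4, the quota table and screener question 1 all use a single 12 to 17 band with 15 places. The only quota comment for this group is about a parent or guardian being present. An age spread is requested for adults alone: "ATTEMPT TO RECRUIT A RANGE OF RESPONDENTS FROM 18-65+ FOR THE ADULTS 18 AND OVER USER GROUP".

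**The concern.** The population named in the objective and the population recruited differ at the lower end, and nothing readable in the protocol limits the conclusion to match. A report that followed section 2.2 and Table 4 literally would claim validation for children aged 0 to 3 without having observed a test on any of them.

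The child's age matters even though the adult is the one scored. Steps 8 and 9 in section 4.5 are carried out on the child, step 8 starts by asking the child to open the mouth wide, and the step provides for the case where the tonsils cannot be swabbed. It is reasonable, though not stated in the protocol, to expect cooperation to vary with the child's age.

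The adolescent point is smaller. The protocol names 12 as the lowest self-testing age but does not ask recruiters to include participants near that age, although it asks for a spread among adults.

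**Working it through.** **The plan's own figure.** Four groups of 15 give 4 × 15 = 60, as section 3.6 states. With the two over-recruits per group in Appendix 3, 4 × 17 = 68. The protocol gives no error rate, threshold or power calculation, so there is nothing further to reproduce.

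**Children: the passages side by side.**

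| Place | Child age range |
|---|---|
| Section 2.6 text | below 12, no lower limit |
| Table 1 | below 12, no lower limit |
| Section 3.6, Table 4 | under 12, no lower limit |
| Appendix 3, quota table | 4 to 11 |
| Appendix 3, question 4 | 4 to 12; under 4 not needed |

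Section 3.1 ties recruitment to Appendix 3, and section 3.7 excludes anyone who does not meet the screening criteria. If the screener is followed, the number of tested children under 4 is 0 of 15. This needs no assumption. Ages 0 to 3 are 4 of the 12 single years below 12, or 4/12 = 33%. That counts years of age and is not a share of users. If a lower limit of 2 applied somewhere unseen, the gap would be 2 of 10 years, or 20%.

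The upper band in question 4 has little effect. Question 4 is reached only after question 3 establishes a child below 12 in the household, so a parent whose only child is 12 never sees it. It still disagrees with the quota table and with section 2.6, which places age 12 among self-testers.

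In the text shown, question 4 records the child's age only as a band, and section 6.1 of the discussion guide asks the participant's own age. The exact age of the tested child is not clearly captured.

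**Adolescents: how likely is a gap?** With n = 15 and a share p of recruits in an age band, the chance that none falls in it is (1 − p)^15. All shares below are assumptions; recruitment is by screener and is not random.

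| Assumption | Event | Probability |
|---|---|---|
| Ages uniform over 12 to 17 | no 12-year-old (2.5 expected) | (5/6)^15 = 6.5% |
| Ages uniform | nobody aged 12 or 13 | (4/6)^15 = 0.23% |
| Ages uniform | all 15 aged 16 or 17 | (2/6)^15 = 7 × 10⁻⁸ |
| 12-year-olds are 10% of recruits | no 12-year-old | 0.90^15 = 20.6% |
| 12-year-olds are 5% of recruits | no 12-year-old | 0.95^15 = 46.3% |
| 80% of recruits aged 16 or 17 | all 15 aged 16 or 17 | 0.80^15 = 3.5% |

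Missing 12-year-olds altogether is plausible under skewed recruitment. Having only the oldest adolescents needs strong selection.

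**The case against.** **The study covers most of the child range, and the adult is the scored user.** Both are true. A reader might infer that the study cannot validate testing of children under 12 at all. The documents do not support that: ages 4 to 11 are recruited, and the gap is confined to ages 0 to 3.

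**Children under 4 are not formally rejected.** Question 4 calls them not required, whereas other questions instruct the recruiter to terminate. A parent of a younger child could still join as an adult self-tester. This stands, but it adds no test on a child under 4.

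**The instructions for use may state a lower limit.** The copy in Appendix 1 is largely unreadable in the text available, so this cannot be ruled out. Even if it does, section 2.6 and Table 4 would still need to agree with Appendix 3.

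**Adolescents aged 12 are eligible.** This stands. A reader might infer that self-testing from age 12 cannot be validated, but the band includes 12-year-olds, and section 6.1 asks each participant's age, so the ages achieved can be reported. The documents support only the statement that coverage of the youngest is not assured.

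**Error rates are biased downward.** A reader might also infer this from the missing ages. The protocol plans no error-rate estimate; section 4.11 classifies each task and investigates causes. That the omitted ages are harder is plausible but not documented, and step 8 already has a fallback when the throat cannot be swabbed.

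**Conclusion.** The child-age mismatch holds on the face of the protocol. The objective and Table 4 reach all children under 12, recruitment starts at 4, and the planned sample has 0 of 15 children aged 0 to 3. No conclusion for those ages can rest on this study. This assumes only that the screener is applied as written and that no lower limit sits in the unreadable part of Appendix 1; such a limit would shrink or remove the gap in the claim but leave the passages to be reconciled.

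The adolescent point is secondary. Coverage of the youngest self-testers is left to chance: the probability of recruiting no 12-year-old is 6.5% with uniform ages and 20.6% to 46.3% if they form 10% to 5% of recruits, all on assumed shares.

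**What to change.** 1. State in section 2.2, section 3.6 with Table 4, and the study report that the caregiver-for-child conclusion covers ages 4 to 11, and that none is drawn for children under 4. Section 2.6 and Table 1 define the product's intended users; whether to change them is for the sponsor and should not be settled by the sample.
2. Correct the upper band in screener question 4 to 4 to 11, in line with the quota table.
3. Record the age of each tested child, so that coverage within 4 to 11 can be reported.
4. Extend the instruction to seek a range of ages to the adolescent group, naming the youngest ages, and report the ages achieved. The documents give no basis for a fixed minimum per age band. Separate bands would also say little: with zero errors, the one-sided 95% upper bound on the error rate is 1 − 0.05^(1/15) = 18.1% for 15 participants and 1 − 0.05^(1/7) = 34.8% for 7.

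The cost is some rewording and one recorded item. The sample size stays at 60. The downside is a narrower claim for children and slightly harder adolescent recruitment.

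### The adult-dependant group is defined by inability to self-test, but the screener and session-start questions neither require nor record it, so Steps 8 and 9 may not carry over to those adults

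*Protocol*

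**What the plan says.** Section 2.6 gives the condition twice. The text says "Adult caregivers will also undertake the test on other adults who are unable to perform the test on themselves", and the matching row of Table 1 reads "Naive adult users to administer the test to other adults who are unable to self-test".

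Later descriptions do not carry it. Table 4 in section 3.6 gives the group as "15 caregivers plus 15 dependants". The quota table in Appendix 3 asks for "Adults who provide caregiver role to another adult and provide assistance". Screener Q5 is "Do you provide a caregiving role to another adult and provide assistance to them" and Q6 is "Do you provide assistance in assisting them to take medication"; both are yes/no items with no stated consequence for either answer. The instruction after Q6 is "TARGET 15 TESTS WHERE TEST IS ADMINISTERED ON THE ADULT DEPENDENT", with no condition on the dependant. Q21 asks only whether the caregiver is willing to perform the test.

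Section 3.7 makes the screening criteria the gate: whoever fails them is excluded, and nothing else is named as a filter.

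**The concern.** The primary objective (section 2.2) is validation in the intended user population. Inability to self-test is what separates this group from one adult swabbing any other adult. If recruitment does not apply the condition, the quota can be filled in good faith with pairs outside Table 1. If nobody records it, the pairs inside and outside cannot be separated afterwards.

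This could matter at Steps 8 and 9 of Table 8. There the caregiver must swab both tonsils without touching other parts of the mouth, then swab a nostril, with a both-nostrils route if the throat cannot be swabbed. How this goes may depend on why the other adult cannot self-test. The discussion guide tells participants that the study bears directly on release of the kit, so what this group can support should be clear.

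**Working it through.** **The plan's own figure.** Section 3.6 states "The total sample size for this study will be 60 participants administering the test". Four groups of 15 administrators give 4 × 15 = 60, which agrees; with 2 over-recruits per group it is 4 × 17 = 68. The protocol gives no power calculation, and none is needed for this point.

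**Search for the condition.** Each place where it could be required or recorded was read.

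| Place | What it asks | Dependant's ability to self-test? |
|---|---|---|
| Appendix 3, inclusion and exclusion lists | Consent, availability, IT, undisturbed room | No |
| Appendix 3, quota row | Caregiver role and assistance | No |
| Q5 | Any caregiving and assistance | No |
| Q6 | Help with medication | Proxy at most; no stated consequence |
| Q8–Q12 | Hand, sight, memory, dexterity | No; put to the respondent, who is the caregiver |
| Q21 | Caregiver's willingness | No |
| Discussion guide 6.1 | Handedness, age, glasses, colour vision, grip | No; about the participant |
| Discussion guide 6.2 | Earlier home tests | No |

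For the child group the screener does restrict the person swabbed: Q4 marks children under 4 as not required. There is no counterpart for dependants.

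**How many pairs are assured.** As written, the number of pairs guaranteed to meet Table 1 is 0 of 15. The actual number, m, can be anything from 0 to 15, and the documents give no basis for estimating it.

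**How much of each session is affected.** Under Table 8 caregivers repeat Steps 1–7 and 10–14 as in the self-test; only Steps 8 and 9 have their own wording. That is 2 of 14 numbered steps, or 2 of 13 because section 6.4 of the discussion guide waives Step 5 when testing someone else. The knowledge questions go to the adult who performed the test.

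**Illustration for Steps 8 and 9 (assumed values, not in the protocol).** Suppose a use error arises only when the dependant cannot self-test, with probability p per such pair. The chance of seeing it at least once is 1 − (1 − p)^m.

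| m | p = 0.05 | p = 0.10 | p = 0.20 | One-sided 95% upper bound if no error is seen, 1 − 0.05^(1/m) |
|---|---|---|---|---|
| 15 | 0.54 | 0.79 | 0.96 | 18% |
| 7 | 0.30 | 0.52 | 0.79 | 35% |
| 3 | 0.14 | 0.27 | 0.49 | 63% |
| 0 | 0 | 0 | 0 | none |

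For example, at p = 0.10 and m = 7, 1 − 0.90^7 = 0.52. The table shows why m needs to be known. It does not predict m or p.

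**The case against.** Five points can be made for the plan.

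**The intended use is broader than Table 1.** Section 2.5 speaks of adults testing children and other adults, with no inability condition, and section 3.2 refers simply to a caregiver and adult group. A caregiver swabbing an able adult is within section 2.5. This stands, and it means the descriptions need reconciling. It does not remove the condition in section 2.6 and Table 1.

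**Q6 may be meant as a dependency filter.** The screener routes one pool of respondents into four quotas, so a 'no' at Q6 could not sensibly end the interview, and the missing termination instruction does not prove that 'no' qualifies. That is fair: Q6 is ambiguous. Even a firm 'yes' would show only help with medication, which is not the same as being unable to swab oneself.

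**The observed user is the caregiver, and the object of study is the kit and its instructions.** This stands, and it confines the consequence mainly to Steps 8 and 9. A reader might infer that sessions with able dependants are uninformative. They are not, since every caregiver still performs the other steps and answers the knowledge questions.

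**Bias is not shown.** A reader might infer that success on Steps 8 and 9 is necessarily overstated because able adults are easier to swab. The documents do not describe the dependants. Someone with poor sight or dexterity may be unable to self-test yet fully cooperative when swabbed by another, and the nostril route means a difficult throat swab need not count as a use error. Upward bias is plausible but not established.

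**A screener question has limits.** A naive caregiver would be judging ability for a test not yet seen. Section 5.2 requires each participant to read and sign consent, so seeking dependants with limited understanding would raise consent questions. Both favour recording the answer and the reason over a hard exclusion.

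**Conclusion.** The point holds in a limited form. Section 2.6 and Table 1 set a condition that the screener and session-start questions neither apply nor record. Nothing scripted would allow the report to say how many of the 15 pairs meet it, and the guaranteed number is zero. Results on Steps 8 and 9 therefore cannot be assumed to apply to adults who cannot self-test.

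This rests on the text alone, and it is not a matter for an analysis plan because eligibility is fixed in the screener. It does not rest on any assumed share of able dependants, for which the documents offer no figure, nor on a claimed direction of bias. It should be corrected, but it affects the swabbing steps in one of four groups and does not invalidate the study.

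**What to change.** Add after Q5 a question on whether the person cared for could take a throat and nose swab on themselves, with the answers yes, only with help, or no, and the reason. Then:

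- give priority in this quota to dependants who could not;
- record the answer for every pair, keeping 'only with help' as its own category because it is looser than Table 1;
- report Steps 8 and 9 for this group split by the answer, and limit any conclusion about adults unable to self-test to those pairs;
- reconcile the descriptions of the group in section 2.5, section 2.6 with Table 1, Table 4, and the quota row and Q5–Q6 of Appendix 3.

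The quota stays at 15 and the total at 60. The cost is one question and possibly slower recruitment for one quota within the five-day window (17 to 21 November 2020). If that is a concern, recording and reporting the answer without giving priority avoids the delay and still shows which pairs support the claim.
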